## **Protocol Summary**

Protocol Number:	HP-00054854
Protocol Title:	Postoperative Heme Oxygenase Induction and Carbon Monoxide Production as a Novel Method to Assess Hepatic Regeneration and Predict Hepatic Related Morbidity After Partial Hepatectomy
Study Rationale:	The goal of this proposal is to elucidate the role of HO-1 induction in hepatic regeneration after partial hepatectomy (PH). There is a growing body of evidence that HO- 1 induction through CO production has an important role in cellular protection and regeneration. To test this concept, we will monitor endogenous CO production in patients who undergo PH and analyze the relationship between CO production and hepatic regeneration. Using this approach we will test the following two hypotheses: (1) HO-1 induction after PH is proportional to 
Study Objectives:	Specific Aim 1: To monitor the extent of HO-1 induction (by measuring endogenous CO production) in relationship to the extent of hepatic resection 1.1 Monitor CO in exhaled air of patients before liver resection, at 4 hours and 24 hours after PH 1.2 Monitor carboxyhemoglobin(COHb) in the arterial blood gas of patients before liver resection at 4 hours and 24 hours after PH 1.3 Analyze the relationship between CO production and the extent of hepatic resection assessed by computed scans liver volumetric study at one and three months after PH, size and weight of the resected specimen and operative report. Specific Aim 2: To analyze the relationship between HO-1 induction and the quality of post-hepatectomy liver regeneration after PH

	
 
2.1 Analyze the relationship between CO production and the quantity and quality of hepatic regeneration assessed by computed scans liver volumetric study at one and three months after PH and liver function tests after PH.
 
2.2 Determine the relation between postoperative liver related morbidity in patients undergoing PH and the extent of postoperative HO-1 induction
 

Study Design:	Study design: Aim 1.1: The monitoring of exhaled CO is based on previous report of assessing exhaled CO in septic patients. Exhaled CO will be determined with an infrared CO analyzer with a sensitivity of 0.1 ppm at 4 hours and 24 hours after PH Aim 1.2: Arterial blood gas (ABG) will be collected from patients before liver resection, at 4 hours and 24 hours after PH. The ABG will be obtained through an arterial line usually placed as part of perioperative monitoring of the patient hemodynamic. This model was found accurate in reflecting HO-1 induction in previous study in patient receiving liver transplantation. Aim 1.3: FLR will be calculated through liver volumetric study from a pre-resectional CT scan. The operative note will be checked for operative details regarding the number of resected hepatic segments and pathological examination of the specimen will allow accurate weight of the resected specimen. According to the resected amount of hepatic parenchyma, three groups of patients will be created (<25%, 25-50% and >50% PH) history of smoking and intraoperative blood transfusion will be reported for each patient. Procedures and Methods - Protocol: For collecting exhaled air specimen, each
	patient will be instructed to exhale completely, and then

take a deep breath, hold it for 20 seconds, and breathe out through D shaped flatpak mouth piece attached to CO analyzer

 
Equipment:
 
A Micro+ CO monitor (Bedfont Scientific Ltd, Wales, England) will be used to analyze CO level in a single breath in exhaled air. The device will be used by applying Anti-bacterial filter and one-way valve for increased infection control.
 
The device has adjustable breath-hold countdown timer for patients who are unable to hold their breath. Calibration will be performed every 6 months as per manufacture recommendation. The device is able to detect and analyze CO concentration within a range of: 0-250 ppm with a sensitivity of 0.1 ppm and accuracy of ±2% in < 20 seconds.
 
Direct evaluation of the COHb level will be performed using an arterial blood gas analyzer (ABL 800 Flex, Radiometer, Copenhagen) and will be reported as % of the total Hb as well as calculated amount in mg/mL.
 


 
Assessment of postoperative liver function and regeneration:
 
Liver volumetry will be measured using image
 
J software downloaded from
 
http://rsbweb.nih.gov/ij/. The accuracy of this method was reported in a prior study.
 
Volumetric study will be performed based on CT scan studies obtained as standard of care preoperatively before each liver resection and at one and three months after each resection.
 
Collected data will be reported as percentage compared to the preoperative hepatic volume.
 
Specific Aim 2: To analyze the relationship between HO-1 induction and the quality of post-hepatectomy liver regeneration
 

 
2.1 Analyze the relationship between CO production and the quantity and quality of hepatic regeneration assessed by computed scans liver volumetric study at one and three months after PH and liver function tests.
 
2.2 Determine the relation between hepatic related morbidity in patients undergoing partial hepatectomy and their ability to induce HO-1
 

Study design: Aim 2.1: As CO is uniquely produced by HO reaction; its level was previously validated to check HO-1 induction. Checking this level and comparing outcome of the previously created three groups of patients (<25%, 25-50% and >50% PH) according to their ability to induce HO-1 after PH. Liver regeneration will be evaluated by radiological criteria at one and three months after PH as described above as well as laboratory criteria including liver function tests. Aim 2.2: HO-1 induction was found to offer beneficial protective effect in different clinical and surgical occasions. In this setting of PH, surgical complications in the perioperative (30 days) period graded by Clavien-Dindo Classification will be reported and analyzed regarding its relation with the ability to induce HO-1.
Procedures and Methods: Liver function tests routinely checked on daily basis till normalization will be monitored. This includes serum protein, Albumin, liver enzymes (AST and ALT), alkaline phosphatase and bilirubin level. The duration needed to this normalization will be checked as well as the trend of each of these laboratory parameters. Hepatic morbidity will be evaluated using the criteria used by the international study group of liver surgery being normalization of the INR and bilirubin by POD#5 while the severity

of post hepatectomy liver failure is graded based on its impact on clinical management. Grade A post hepatectomy liver failure requires no change of the patient's clinical management. The clinical management of patients with grade B post hepatectomy liver failure deviates from the regular course but does not require invasive therapy. The need for invasive treatment defines grade C post hepatectomy liver failure. The Clavien-Dindo classification will be used to document surgical outcome of patients after PH.

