#### Analyses:

All results will be collected in Excel Document. Analyses of groups based on the extent of liver resection and CO production. Results of different subgroups will be analyzed; comparison between groups will be performed by fisher test, paired and unpaired student t test, main Whitney test or ANOVA with repeated measurements when appropriate. Significance is defined as p<0.05.

Potential problems and alternative strategy: It is possible that HO-1 induction varies according to preoperative and intraoperative factors beside the patient own ability to induce HO-1. The most important known other factors are smoking and intraoperative blood transfusion will be reported in the study, however, other factors may exist and influence the result of this study. Preoperative factors may include preoperative use of chemotherapy and the presence of underlying liver cirrhosis. Intraoperative factors may include operative time and surgical technique (open or minimally invasive). In case of significance variance between patient s in the same group (same percentage of PH) Subgroup analysis including different variants (preoperative chemotherapy, perioperative

	blood transfusion and onen vorsus minimally
	blood transfusion and open versus minimally
	invasive technique) will be used to assess the
	effect of these factors.
Study Population:	125 participants enrolled locally; 125
	enrolled worldwide
Inclusion Criteria:	1-Patients plans to have partial liver
	resection for primary liver pathology or
	metastatic disease
	2-Patients able to comprehend and willing to
	sign the written consent form
Exclusion Criteria:	1-Patients with age less than 18 years
	2-Patients identified as part of the vulnerable
	populations as defined in the current
	application, except women with child bearing
	potential with negative pregnancy test
Study Treatment:	For Aim 1, after the patient's procedure, they
	will have to exhale into the device listed for
	collecting exhaled air specimen.
	For Aim 2, the patient's blood samples that
	are routinely collected after a hepatectomy
	will be used for analyzing serum protein,
	Albumin, AST and ALT, alkaline phosphatase,
	and bilirubin level.
	The duration of an individual's participation
	will be about 3 months +/- 2 weeks.
Study Procedures and Assessments:	Aim 1:
	Procedures and Methods
	- Protocol:
	For collecting exhaled air specimen, each
	patient will be instructed to exhale
	completely, and then

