## 2. STUDY OBJECTIVE

The goal of this proposal is to elucidate the role of HO-1 induction in hepatic regeneration after partial hepatectomy (PH). There is a growing body of evidence that HO-1 induction through CO production has an important role in cellular protection and regeneration. To test this concept, we will monitor endogenous CO production in patients who undergo PH and analyze the relationship between CO production and hepatic regeneration. Using this approach, we will test the following two hypotheses: (1) HO-1 induction after PH is proportional to the extent of the surgical resection, and (2) failure to appropriately induce HO-1 is associated with impaired hepatic regeneration.

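### Aim 2.2 relates CO to hepatic morbidity without accounting for extent of resection, and the named tests give no measure of the prediction that the title announces

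*Combined protocol and SAP*

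**What the plan says.** The title calls CO production a "Novel Method to Assess Hepatic Regeneration and Predict Hepatic Related Morbidity After Partial Hepatectomy". The rest of the document is more restrained. Aim 2.2 is to "Determine the relation between hepatic related morbidity in patients undergoing partial hepatectomy and their ability to induce HO-1", and hypothesis 2 (Section 2, Study Objective) is worded as an association.

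The Analyses paragraph of the Protocol Summary, repeated under Statistical Analyses for Aim 1 and Aim 2, says that "comparison between groups will be performed by fisher test, paired and unpaired student t test, main Whitney test or ANOVA with repeated measurements", and that "Significance is defined as p<0.05". It names no regression, correlation coefficient, AUC, sensitivity or specificity, CO cut-off or validation step. The Introduction mentions correlating CO with regeneration, but the analysis text names no method for it.

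On extent of resection, hypothesis 1 states that "HO-1 induction after PH is proportional to the extent of the surgical resection". Patients are placed in three extent categories (below 25%, 25-50%, above 50%). The analysis text refers to "Analyses of groups based on the extent of liver resection and CO production". The study design for Aim 2.1 (regeneration) compares outcome in the three extent groups by ability to induce HO-1, without defining that ability. Nothing equivalent is written for Aim 2.2 (morbidity). The planned subgroup analyses are conditional and cover chemotherapy, transfusion and open versus minimally invasive technique.

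**The concern.** There are two gaps.

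**Confounding by extent.** The protocol's own first hypothesis ties CO to extent. If larger resections also carry more hepatic morbidity (an assumption, since the documents give no rates), extent drives both sides of the Aim 2.2 comparison. An unadjusted test could show a CO difference that is only extent. It could also hide or reverse the protective relation the investigators expect, because larger resections would bring both more CO and more morbidity.

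**A p value does not measure prediction.** A significant difference in mean or rank says little about how well CO separates patients who develop liver failure from those who do not. With few events, a just-significant result corresponds to modest separation with a wide interval. Without an AUC and its interval, a reader cannot tell whether the word in the title is earned.

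**Working it through.** **Inputs.** From the documents: N = 125 ("125 participants enrolled locally; 125" worldwide) and a 0.05 threshold, taken as two-sided because sidedness is not stated. No power, effect size, SD or event rate accompanies the 125, so it cannot be reproduced. Assumed: liver failure in 10-15%, i.e. 12 to 19 of 125, with 8 and 25 events as a wider range.

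**Step 1. AUC at which Mann-Whitney just reaches p = 0.05.** With e events and m = 125 − e non-events,

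AUC = 0.5 + 1.96 × √[(N + 1)/(12·e·m)].

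- e = 12, m = 113: √[126/(12 × 1356)] = 0.0880, so AUC = 0.5 + 0.172 = 0.672.
- e = 19, m = 106: √[126/(12 × 2014)] = 0.0722, so AUC = 0.642.
- e = 8: 0.708. e = 25: 0.627.

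The Hanley-McNeil variance is [A(1−A) + (e−1)(a−A²) + (m−1)(b−A²)]/(e·m), with a = A/(2−A) and b = 2A²/(1+A). It gives 95% CIs of 0.50 to 0.85 at 12 events and 0.50 to 0.79 at 19.

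**Step 2. What that means for classification.** Assume equal-variance normal CO. The smallest significant standardised difference is d = t(0.975; 123) × √(1/e + 1/m), which is 0.60 at 12 events and 0.49 at 19. At 80% specificity, sensitivity = Φ(d − 0.842).

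- 12 events: sensitivity 40.5%; PPV = 0.405 × 0.096/(0.405 × 0.096 + 0.2 × 0.904) = 17.7%.
- 19 events: sensitivity 36.4%; PPV = 0.364 × 0.152/(0.364 × 0.152 + 0.2 × 0.848) = 24.6%.

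**Step 3. Can extent alone produce a significant CO difference?** Simulation with N = 125. Extent is standard normal, CO correlates with extent at ρ, and morbidity depends on extent only (logit intercept −2, odds ratio 2 or 3 per SD). CO therefore adds nothing beyond extent. Averaging the logistic function over extent gives event rates of about 14% and 16%. All of these settings are assumptions. The unadjusted t test used 2000 runs and ordinary logistic regression on extent plus CO used 500.

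| ρ | Unadjusted, OR 2 | Unadjusted, OR 3 | Adjusted, OR 2 | Adjusted, OR 3 |
|---|---|---|---|---|
| 0 | 5.0% | 4.7% | 5.2% | 4.4% |
| 0.3 | 13.1% | 22.1% | 4.4% | 5.0% |
| 0.5 | 21.8% | 48.6% | 5.2% | 5.8% |
| 0.7 | 42.0% | 76.0% | 5.0% | 5.4% |

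With 500 runs the Monte Carlo standard error of the adjusted figures is √(0.05 × 0.95/500) ≈ 1 percentage point, so they are consistent with 5%.

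**The case against.** Several stronger readings are tempting, and the documents do not support them.

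- *That prediction is the study's question.* The word is in the title only; the aims and hypotheses concern a relation or association. Retitling would close that part of the gap. It would not cure the confounding, which affects an association just as much.
- *That extent is ignored.* It is not. The Aim 2.1 design compares outcome in the three extent groups by HO-1 induction, and the analysis text groups by extent and CO production. On a generous reading this extends to morbidity. Even so, induction is undefined and no method combines the strata. With 12 to 19 events, three strata would hold on average only 4 to 6 each (12/3, 19/3).
- *That extent is known before any CO sample.* A pre-resection CO sample is planned, and achieved extent comes later. The point concerns the postoperative samples.
- *That morbidity is not an outcome.* The Study Endpoints list, headed for Aim 1 only, omits it. However, 30-day Clavien-Dindo complications and graded liver failure are specified for Aim 2.
- *That the study cannot speak to its title at all, or that a significant result means almost no discrimination.* The Mann-Whitney statistic divided by e·m is the AUC, so discrimination can be recovered from planned data. The lower confidence limit lies near 0.50 by construction at p = 0.05, and point estimates of 0.64 to 0.67 are weak, not nil.

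It is also fair to say that 12 to 19 events cannot support a full prediction-model exercise. Calibration and change in AUC would be very imprecise.

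**Conclusion.** The point holds in a limited form. The title goes further than the aims and the named tests, and Aim 2.2 has no extent-adjusted analysis although hypothesis 1 makes extent an expected driver of CO.

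Under the assumed odds ratios and correlations of 0.3 to 0.7, the unadjusted t test is significant in 13% to 76% of trials when CO adds nothing beyond extent, against about 4% to 6% with adjustment. At zero correlation there is no inflation, so the size depends on how closely CO follows extent.

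A just-significant result corresponds to an AUC of about 0.64 to 0.67 if liver failure occurs in 10-15%, about 0.71 at 8 events and 0.63 at 25. The event rate is assumed and covers liver failure only; the documents give no rate for Clavien-Dindo complications either.

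A reader might infer that a significant difference will be reported as prediction. The documents do not say so. What they lack is the analysis that would allow the claim to be judged.

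**What to change.** For Aim 2.2, pre-specify:

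1. One postoperative CO measure and time point, and its AUC with 95% CI against liver failure.
2. One penalised (Firth) logistic model for liver failure with two predictors, continuous extent of resection and that CO measure. Report the CO odds ratio with CI and the likelihood-ratio test against extent alone.
3. A rule for wording. Use 'predict' only with the AUC and its CI reported, and claim added value only if CO contributes beyond extent. Otherwise word the title and conclusion as 'associated with'. The two claims should stay separate, because a marker can predict an outcome without adding to another marker.

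CO, resected extent and liver failure are already to be collected, so the cost is a little more analysis. The downside is a more modest headline with a wide interval, because events are likely to be few.

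### Aim 1.3 hypothesises proportionality between HO-1 induction and extent of resection, but the plan names only three-group comparisons and specifies no estimate of CO change per percent of liver resected

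*Combined protocol and SAP*

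**What the plan says.** Section 2 (Study Objective) states the first hypothesis: "HO-1 induction after PH is proportional to the extent of the surgical resection". The matching objective, Aim 1.3 in the Protocol Summary, is to "Analyze the relationship between CO production and the extent of hepatic resection", with extent "assessed by computed scans liver volumetric study at one and three months after PH, size and weight of the resected specimen and operative report".

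The Study Design text for Aim 1.3 describes continuous sources for extent: "FLR will be calculated through liver volumetric study from a pre-resectional CT scan", and "pathological examination of the specimen will allow accurate weight of the resected specimen". It then turns extent into categories: "three groups of patients will be created (<25%, 25-50% and >50% PH").

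The Analyses paragraph, repeated for both aims under Statistical Analyses, takes the group as its unit: "Analyses of groups based on the extent of liver resection and CO production". The methods follow: "comparison between groups will be performed by fisher test, paired and unpaired student t test, main Whitney test or ANOVA with repeated measurements", to be chosen when appropriate, with significance at p<0.05. The sample size is 125. No effect size, standard deviation, expected distribution of extent or power statement is given.

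**The concern.** A proportionality hypothesis is about a rate: how much CO production rises for each additional percent of liver removed. Three bins with between-group tests do not supply that rate. They treat a 26% and a 49% resection as the same exposure, and a 24% and a 26% resection as different ones. The result is a set of group differences, which cannot readily separate a steady gradient from a threshold.

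The study could therefore finish with a significant group comparison and still lack the quantity in its first hypothesis, although the data for it are on file. A slope added after the data are seen would be a post hoc choice, since the plan already leaves the selection among several tests open.

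**Working it through.** **Is a slope specified anywhere?** The wording that might cover it does not.
- The Aim 1.3 objective speaks of analysing a relationship but names no method.
- The Introduction speaks of correlating CO, but with the rate of liver regeneration and with liver function, which is Aim 2.
- The Aim 2 procedures mention a trend, but of laboratory values over time.
- Repeated-measures ANOVA by group adds the time dimension; it gives no slope on extent.

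The plan does not exclude a slope or trend analysis, but it specifies none.

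**What the choice is worth.** The documents give no figure to reproduce, so this is illustration. From the documents: n = 125, alpha 0.05 (two-sided assumed), cut-points 25% and 50%. Assumed: the true relation explains R² = 0.0625 of the variance in a single CO value (r = 0.25 if linear), under three distributions of percent resected:
- A: uniform 5–75% (SD 20.2; groups 29/36/36%)
- B: 5 + 75 × Beta(1.5, 2) (SD 17.5; groups 29/45/26%)
- C: normal, mean 35, SD 18, truncated to 5–80% (SD 15.8; groups 26/54/21%)

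*Precision of the slope if linear.* The slope per 10 points is 0.25 × 10/SD: 0.12, 0.14 and 0.16 SD of CO for A, B and C. The 95% half-width is t(0.975; 123) × √((1 − 0.0625)/123) × 10/SD = 1.979 × 0.0873 × 10/SD: 0.086, 0.099 and 0.109. The named group tests give no counterpart to these figures.

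*Power.* Noncentral F with λ = n·R²/(1 − R²).
- Slope: R² is 0.0625 times the squared correlation of the true shape with extent; df 1, 123. If linear, λ = 125 × 0.0625/0.9375 = 8.33, power 81.7%.
- ANOVA: R² is 0.0625 times the share of the shape's variance lying between groups; df 2, 122. If linear under A that share is 0.886, so R² = 0.0554, λ = 7.33, power 66.5%.

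| True shape | Slope, A/B/C (%) | Three-group ANOVA, A/B/C (%) |
|---|---|---|
| Linear | 81.7 / 81.7 / 81.7 | 66.5 / 64.8 / 62.9 |
| Plateau from 40% | 72.1 / 71.9 / 71.7 | 64.8 / 62.8 / 60.9 |
| Hinge at 40% | 72.1 / 69.3 / 66.5 | 63.2 / 62.0 / 60.5 |
| Plateau from 25% | 54.2 / 50.4 / 48.2 | 53.9 / 51.3 / 49.6 |
| Step at 50% | 65.3 / 59.9 / 54.5 | 72.5 / 72.5 / 72.5 |
| Step at 25% | 60.0 / 56.3 / 53.7 | 72.5 / 72.5 / 72.5 |

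*With pre-resection CO as covariate.* Simulation, 3,000 trials per cell; equal effect at 4 h and 24 h, none at baseline; the 4 h value analysed; within-patient residual correlation 0.3 or 0.6.
- Linear: slope 83–84% or 94%; three-group ANCOVA 66–70% or 82–84%.
- Step at a cut-point: slope 57–69% or 70–82%; ANCOVA 74–77% or 89–90%.
- Repeated-measures ANOVA, group-by-time over three time points: 47–53% or 76–80% if linear; 57–60% or 84–86% for a step.

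The ordering is the same as for a single value.

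**The case against.** **Groups already inform the question.** Three ordered means are a coarse picture of how CO changes with extent, and the list of tests is not said to be exhaustive. Both are true. What is missing is narrower: a pre-specified rate per percent resected, with its uncertainty.

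**Part of the power gap is not due to binning.** The comparison sets a 1-df test against a 2-df omnibus test. A 1-df trend test on the same three groups (scores 0, 1, 2) has about 73–77% power in the linear case, so binning itself costs about 5–8 points and the rest comes from the untargeted test. This stands. But the plan names no trend test either, and a trend test would still give no slope per percent.

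**Power does not settle the choice.** This also stands. With a step at a cut-point the ANOVA leads by about 7–19 points, so the case rests on the missing estimate.

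**A slope alone does not prove strict proportionality.** Correct: that also requires the change from baseline to pass through zero at zero resection. The fix asks for that intercept before the claim is made.

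**The baseline covariate may not exist for exhaled CO.** The Study Design text for Aim 1.1 and the Study Endpoints list only 4 and 24 hours. However, the Study Objectives and Sections 6 and 7 plan a pre-resection measurement, and the Aim 1.2 design text does so for arterial blood gas. The baseline is planned; the shorter lists should be aligned with it.

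**Conclusion.** The concern holds. The plan's first hypothesis is a dose-response statement, and no analysis in the plan is specified to estimate that dose-response. This follows from the text and does not depend on any calculation.

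The power figures are secondary and rest on an assumed effect size, shape and distribution of extent. They show a gain of about 15–19 points from a slope test if the relation is linear, 6–11 points for a plateau or hinge at 40%, rough equality for a plateau at 25%, and a loss if CO steps exactly at a cut-point. No fixed loss of sample size can be claimed. The omission is recoverable because the continuous data are kept, but it should be corrected before analysis so that the slope is not a post hoc result.

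**What to change.** For Aim 1.3 only:

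1. Make the main analysis a linear regression of postoperative CO on percent of liver resected as a continuous variable, adjusted for the pre-resection CO value. Report the slope with its 95% CI.
2. State beforehand which pre- or intraoperative measure defines percent resected. It should not be the one- and three-month volumes listed in Aim 1.3, because the plan uses those to measure regeneration.
3. State which CO measure (exhaled CO or COHb) and which time point this model uses.
4. Pre-specify a linearity check (quadratic or spline term) and show the fitted curve with its CI.
5. Claim strict proportionality only if the intercept of a change-from-baseline model is also reported with its CI.
6. If smoking is a covariate, name it beforehand. Use transfusion only in a sensitivity analysis, since it may be a consequence of resection size.
7. Keep the three groups as a secondary comparison for Aim 1.3, and unchanged for Aim 2.1 and for the subgroup analyses under potential problems.

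The cost is revised wording and these definitions; no new data or visits. The downside is reliance on approximate linearity. Under the same assumptions (n = 125, R² = 0.0625) a quadratic term has only 14–26% power to detect a step at 25% or 50%, and 24–32% for a plateau or hinge at 40%. A non-significant check therefore does not establish linearity, which is the reason to retain the group comparison.

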	classification will be used to document
	surgical outcome of patients after PH.
Study Endpoints:	Aim 1:
	-CO output/production based on extent of
	liver resection, to be collected at 4 hrs and 24
	hrs after PH
	-CT scans looking at hepatic regeneration and
	one and three months after PH and liver
	function tests
Statistical Analyses:	Aim 1 Analyses:
	All results will be collected in Excel
	Document. Analyses of groups based on the
	extent of liver resection and CO production.
	Results of different subgroups will be
	analyzed; comparison between groups will be
	performed by fisher test, paired and
	unpaired student t test, main Whitney test or
	ANOVA with repeated measurements when appropriate. Significance is defined as
	p<0.05.
	ρ<0.05.
	Aim 2 Analyses:
	All results will be collected in Excel
	Document. Analyses of groups based on the
	extent of liver resection and CO production.
	Results of different subgroups will be
	analyzed; comparison between groups will be
	performed by fisher test, paired and
	unpaired student t test, main Whitney test or
	ANOVA with repeated measurements when
	appropriate. Significance is defined as
	p<0.05.
Study Duration:	15 years

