## 3. INVESTIGATIONAL PLAN

This is a University of Maryland Medical System multi-site study being done at University of Maryland Medical Center and UM Baltimore Washington Medical Center.

The study will monitor carbon monoxide production in patients undergoing liver resection and aims to identify the relationship between CO production and recovery after this resection.

Carbon monoxide will be checked from arterial blood gas obtained routinely as a part of the postoperative care as well as from the exhaled air of the patient through a CO detector commercially available and used as smokerlyzer helping people to stop smoking. The results of the surgical resection will be collected from the patient routinely ordered tests after liver resection including pathology of the resected part of the liver, laboratory and radiology tests.

The study duration for each individual patient is approximately 3 months +/- 2 weeks.

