# 6. STUDY VISITS

Patients planned to undergo partial hepatectomy for primary or metastatic hepatic pathology will be screened for eligibility to participate in this study. Objectives, methods of data

collection, and analysis will be discussed. After answering all patient questions and explaining the patient rights including refusal to participate, the patient will be offered to participate in the study. Patients who will accept to participate will be asked to sign the participation consent form. It is a prospective data collection without interference with the treatment plan.

For Aim 1, CO will be monitored before a patient's liver resection, and at 4- and 24-hours post-resection.

For Aim 2, CT scans of liver volume will be performed at one and three months posthepatectomy, as well as liver function tests PH.

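### Smoking is recorded as a history only, with no current status or time since the last cigarette, so recent tobacco CO can distort the measure of HO-1 induction in either direction

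*Combined protocol and SAP*

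**What the plan says.** The Protocol Summary, Study Design, Aim 1.3, states that "history of smoking and intraoperative blood transfusion will be reported for each patient". The Analyses section adds, under potential problems: "The most important known other factors are smoking and intraoperative blood transfusion will be reported in the study". Neither place defines categories, current use or recency, and no other section does.

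Smoking then drops out. The fallback for unexplained variation within a resection group, "Subgroup analysis including different variants (preoperative chemotherapy, perioperative" and so on, continues with transfusion and surgical technique. It does not name smoking, and no adjusted model is planned. Sections 5.1 and 5.2 do not exclude smokers.

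On measurement, section 3 describes the breath device as "a CO detector commercially available and used as smokerlyzer helping people to stop smoking". Section 6 says "CO will be monitored before a patient's liver resection, and at 4- and 24-hours post-resection", and section 7 agrees for both breath CO and COHb. The Aim 1.1 design text, however, gives only the later times: "Exhaled CO will be determined with an infrared CO analyzer with a sensitivity of 0.1 ppm at 4 hours and 24 hours after PH". The Aim 2.1 design text justifies the marker thus: "As CO is uniquely produced by HO reaction; its level was previously validated to check HO-1 induction". The Study Endpoints entry lists CO at 4 h and 24 h. No section says whether induction is a change from the pre-resection value, a post-operative level or a threshold.

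**The concern.** The marker stands for HO-1 activity only if the measured CO is endogenous. Inhaled tobacco CO breaks that premise, but only in people who smoked recently. A history of smoking is positive both for someone who stopped years ago and for someone who smoked the day before surgery, and only the second carries tobacco CO into the pre-resection sample. The item collected therefore cannot identify the patients whose readings are contaminated.

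Two things are at stake. The Aim 1 relation between CO change and extent of resection gains noise. In Aim 2, a smoking-driven shift in apparent induction could be mistaken for biology if current smokers also differ in outcome.

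**Working it through.** The plan offers no figure to reproduce. Its 125 participants come with no SD, effect size, smoking prevalence, tobacco CO level or clearance rate. Everything numerical below is an assumption shown over a range.

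**1. Direction and size in one current smoker.** Let x be the tobacco excess at the pre-resection sample (COHb points), h the half-life in hours, and t the time of the later sample, with no smoking in between.

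- Bias in the post-operative level: x·0.5^(t/h)
- Bias in change from baseline: x·0.5^(t/h) − x

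Example, x = 2, h = 8, t = 4: 2 × 0.5^0.5 = 1.41, so the level is +1.41 and the change is 1.41 − 2 = −0.59.

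| x | h | level, 4 h | change, 4 h | level, 24 h | change, 24 h |
|---|---|---|---|---|---|
| 1 | 2 | +0.25 | −0.75 | 0.00 | −1.00 |
| 1 | 8 | +0.71 | −0.29 | +0.12 | −0.88 |
| 2 | 2 | +0.50 | −1.50 | 0.00 | −2.00 |
| 2 | 8 | +1.41 | −0.59 | +0.25 | −1.75 |
| 4 | 2 | +1.00 | −3.00 | 0.00 | −4.00 |
| 4 | 8 | +2.83 | −1.17 | +0.50 | −3.50 |

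The change score is always biased down and the level never is. At 24 h at most 0.5^(24/8) = 0.125 of the excess remains. A former smoker has x = 0 and no bias on either scale. The clock starts at the pre-resection sample; counting operating time as well would push the 4 h change bias further down and the 4 h level bias toward zero.

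**2. Why a history flag does not repair it.** Take x = 2, h = 5, t = 24, and suppose 35% of patients with a positive history smoke currently. The change bias in current smokers is −2 × (1 − 0.5^4.8) = −1.928. The flag's mean bias is 0.35 × (−1.928) = −0.675. Adjusting for the flag leaves −1.928 + 0.675 = −1.253 in current smokers and moves former smokers by +0.675.

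**3. Noise in Aim 1.** Assume 10–20% current smokers (12.5 to 25 of 125), x = 1.5 to 3, 5–20% of it left at 24 h, and a true mean rise of 0.3. Current smokers then change by 0.3 − 1.5 × 0.80 = −0.9 to 0.3 − 3 × 0.95 = −2.55. With induction SD 0.4 and assay SD 0.1, the SD of change without tobacco is √(0.16 + 2 × 0.01) = 0.42. Let p be the share of current smokers and D the mean tobacco shift, with the excess varying between smokers by 40% of its mean. The variance becomes 0.18 + p(1−p)D² + p(0.4D)²:

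- p = 0.1, D = 1.2: 0.18 + 0.130 + 0.023 = 0.333, SD 0.58
- p = 0.2, D = 2.85: 0.18 + 1.300 + 0.260 = 1.740, SD 1.32

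Simulation gave 0.57 to 1.38. For one assumed slope (0.006 COHb points per percent resected, 10% of the excess left at 24 h, n = 125), simulated power on the change score was 19–55% adjusting for ever-smoking and 45–75% adjusting for current smoking. With 24 h CO adjusted for pre-resection CO it was 69–73% and 70–78%.

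**4. Spurious link with complications (Aim 2.2).** Simulated with no true link, 35% former smokers, and an assumed complication risk of 25% in non-smokers and 35–40% in current smokers. Odds ratios are per SD lower apparent induction; error rates are at n = 125 and nominal 5%.

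| Analysis | OR | False positives |
|---|---|---|
| Change, unadjusted | 1.10–1.28 | not recorded |
| Change, ever-smoking | 1.09–1.26 | 6–21% |
| Change, current smoking | 0.98–1.01 | 3–6% |
| 24 h level, no smoking variable | 0.89–0.98 | 4–9% |
| 24 h level given pre-resection CO, no smoking variable | about 1.04 | 4–5% |

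With equal complication risk in smokers and others, the link on the change score vanished. The 4 h reading was not simulated.

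**The case against.** A reader might infer that tobacco washout will be scored as failure to induce HO-1. The documents contain no such scoring rule. The endpoint entry lists the 4 h and 24 h values, Aim 2.1 speaks of a CO level, and the listed tests include unpaired t and Mann-Whitney as well as paired t and repeated-measures ANOVA. On the post-operative level the bias reverses or is small. Change remains the natural reading of a pre-resection sample combined with paired or repeated-measures tests, but it is only a reading.

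A reader might also infer that the error favours hypothesis 2. That hypothesis (section 2) concerns regeneration, whereas the simulated link is with complications under an assumed excess risk in smokers. Nothing here shows that smoking shifts CT volume or liver function results, so that inference is not supported. Nor does the plan state that former and current smokers will be merged; it leaves the item undefined. The ever-smoking model in steps 3 and 4 is illustrative and not part of the plan.

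The strongest point that stands is that the pre-resection reading is itself an objective marker of recent smoking. Adjusting for it brings the Aim 2.2 error rate to nominal and recovers most of the Aim 1 power. Recording recency therefore adds less than the change-score figures suggest. It is still needed, because the pre-resection value mixes tobacco and endogenous CO, the plan specifies no baseline adjustment, and the Aim 1.1 text leaves the breath baseline unclear.

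**Conclusion.** The gap is real and worth closing, though not fatal. As written, the plan leaves recent tobacco CO in its induction measure, with no variable to identify it and no analysis to separate it. The direction depends on a definition that the plan does not give: downward on change from baseline; upward at 4 h and near zero by 24 h on the post-operative level. Added noise in Aim 1 on a change score follows whenever some participants smoked shortly before the pre-resection sample. The Aim 2.2 distortion needs both a change score and a higher complication risk in current smokers. All sizes rest on assumed prevalence, tobacco excess, washout and risk, none of which the documents supply.

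**What to change.** - Replace the smoking item with never / former / current, plus hours since the last cigarette, asked when the pre-resection sample is taken.
- Define the induction analysis as post-operative CO adjusted for pre-resection CO and current smoking, instead of raw change. Confirm in the Aim 1.1 text that breath CO is also read before resection.
- Repeat the Aim 1 and Aim 2 CO analyses without patients who smoked within 24 h before the pre-resection sample.

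The cost is two form questions, one model specification and one sensitivity analysis; care is unaffected. Self-report may understate recent smoking, and the sensitivity analysis uses fewer patients. Hours since the last cigarette cannot be reliably recovered afterwards, so for anyone already enrolled only the adjustment for pre-resection CO is likely to be available.
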